The risks of photography and imaging are the same for all three imaging modalities used: close-range clinical photography (Nikon D7200), 3D Photography (Vectra H2), and the VISIA and/or VISIA-CR. Photographs include a risk of identification, as these will be full face photos. Privacy will be protected to the greatest extent possible. Photos will only be identified by unique subject identification number that contains no personal identifying information. All photos will be stored on a password secure drive, with only access by research personnel. For research purposes, photos may be used in scientific publications.

Adverse Events

At each visit, a member of the research team will question the subject about adverse events using an open-ended question. If a potential adverse event is reported by the subject or identified during examination, directed questioning and examination will be performed when appropriate. At this time, the following will be performed:

1. Obtain a complete history of the event in question as well as conduct an examination of the subject and determine if the reported event qualifies as an Adverse Event (AE). If the event is determined to be an AE, an AE case report form and Event Follow-up (EF) visit case report form must be completed. One AE case report form should be used to track the history of an individual AE throughout the period of the study.
2. Collect an updated medical and surgical history along with recording of concomitant medications or treatments.
3. Take photographs of the subject with attention to the area in question.
4. Render treatment for the event, if any, as determined by the medical judgement of the Investigator.

Photographs will be taken to document any AEs if possible.

For the duration of the study, medical assistance will be provided to the subject for study-related problems at no expense, if in the opinion of the Investigator, the reaction was caused by MOXI treatments. Should a subject choose to seek their own medical treatment, no reimbursement will be offered.

When an AE persists at the end of the study, the Investigator will ensure a follow-up of the subject until the Investigator believes that the event is satisfactorily resolved.

Subject Safety and Data Monitoring

Research Standards and Good Clinical Practice

The conduct of this study will follow all applicable guidelines for the protection of human subjects for research as outlined in 21 CFR 50, in accordance with the accepted standards for Good Clinical Practice (GCP), International Conference on Harmonization (ICH), and the standard practices of UT Southwestern.

Data Monitoring

For this protocol, which involves the use of a non-significant risk device, the Investigator will monitor accrual, subject experience, attrition, patterns of adverse events and/or unexpected adverse events, any protocol deviations, or violations any changes in the risk/benefit analysis.

Subjects will be asked about any adverse events throughout the study. Subjects will be asked to contact the Investigator if adverse events develop between visits. If necessary, an unscheduled visit will be arranged so that the Investigator can clinically evaluate and photograph these findings.

Procedures to Maintain Confidentiality

All study records and information will be identified by the subject number. All subject identifiers will be removed from all documents. The link between subject name and study ID number will be kept in separate password-protected files. Documents containing identifying information will be kept in locked files in the research staffs' locked office. All electronic study data will be password protected with access limited to members of the research team. No direct identifying information will be shared with any outside entities. Electronic data (electronic data entry - Case Report Forms) will be password protected.

Photographs of subject's faces will be taken at enrollment, treatment, and follow-up visits. These photographs will be identified by subject numbers. Subject confidentiality will be protected to the greatest extent possible

This study will be performed in accordance with Health Insurance Portability and Accountability Act. These guidelines will be followed specifically with regard to the privacy and confidentiality of patient care and study records. Personnel associated with Investigator's office, the U.S. Food and Drug Administration (FDA) and the governing Institutional Review Board, have the right to review the data, including photographs, collected during this study.

References

1. Kaufman, B.P., T. Aman, and A.F. Alexis, *Postinflammatory Hyperpigmentation: Epidemiology, Clinical Presentation, Pathogenesis and Treatment*. Am J Clin Dermatol, 2018. **19**(4): p. 489-503.

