The primary objective of this study is to quantify the hyperpigmentation response after 1927nm non-ablative fractionated laser therapy in subjects with Fitzpatrick Skin Phototypes V and VI and explore an effective, adjunctive pre- and post-procedural topical regimen to prevent iatrogenic dyspigmentation or scarring in this population.

We will explore this question with a non-blinded, observational study at a single center.

Clinical Study Design

Overview of Clinical Study

This is a single-site, prospective observational, non-randomized, non-controlled pilot study being conducted at the University of Texas Southwestern Medical Center at Dallas in the Department of Plastic Surgery. The study is designed to follow changes in hyperpigmentation in approximately 20 qualified and consenting subjects receiving f1927 hyperpigmentation standard care treatment using VISIA and/or VISIA-CR. The Principal Investigators (PIs) have been selected based on their expertise, qualifications, subject access, prior clinical research, facilities, and interest in this field of research. Subjects will be recruited through IRB-approved advertisements or identified by [name] at the University of Texas Southwestern Medical Center. Subjects will be numbered sequentially in the order in which they initially qualify for entry into the study. Subjects who continue the study from Part 1 will retain their subject number through Part 2. Any new subjects recruited for Part 2 will be numbered sequentially in the order they qualify for entry into the study.

Part 1:

Study doctors will explain and prescribe subjects a standard of care topical regimen 4-6 weeks prior to f1927 treatments.

Part 2:

Subjects will be asked to complete a month-long washout period of all topical regimens prior to f1927 treatments. Following each treatment subjects will be asked to apply Clobetasol twice a day for four days and apply ice to the treated areas four times a day.

Clinical Treatment and Assessments

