Participating subjects will receive treatment using an FDA-approved f1927 laser, currently considered a standard of care treatment for melasma and hyperpigmentation in Fitzpatrick Skin Phototypes I-VI. Subjects will undergo treatments over the entire face. Subjects' response to effects of the f1927 treatment will be quantified based on evaluation of standard and clinical photography and H2 3D Imaging System images taken pre- and post-procedure. These photos will be identifiable full-face photos, and subjects will be adequately informed and consent of such. In addition to the two standard care photographic assessments, subjects will also have photos taken using the VISIA and/or VISIA-CR (Canfield Scientific, Fairfield, NJ). A quantitative assessment of the effects of treatment will be performed using VISIA and/or VISIA-CR at 1-month and 3-months post-treatments. Additional assessment will be provided by use of the Skin Hyperpigmentation Index (<https://shi.skinimageanalysis.com/> - Inselspital, Freiburgstrasse, Switzerland) [12-15] a web-based software used to quantify hyperpigmentation. Changes in the Skin Hyperpigmentation Index over time will be used to objectively report on subjects' treatment response.

From these procedures, the improvement in diffuse pigmentary changes can be evaluated in comparison to pre-treatment assessments.

Primary Endpoints

1. Quantifying Improvement in overall facial hyperpigmentation in response to laser treatment, by measuring pigmentation at baseline and follow-up visits post-treatment using the VISIA and/or VISIA-CR
2. Changes in Skin Hyperpigmentation Index (SHI) Scores from Baseline to post-treatment visits..

Secondary Endpoints

1. Monitoring incidence, severity, and relatedness of adverse events throughout the study
2. Monitoring the efficacy of pre- and post-treatment regimens with tretinoin and hydroquinone
3. Monitor the efficacy of the pre- and post-treatments with Clobetasol and ice.

Standard of Care Treatment Device

Proprietary Name	Device Description	Regulatory Information
Sciton MOXI	Aesthetic device that utilizes a fractionated laser to initiate resurfacing for the treatment of dyspigmentation and healing of photoaged skin.	Class II 510(K) Number: N/A Regulation Number: 878.4810

Study Population, Screening, and Enrollment

Study Population

The study population in question includes patients ages 18-75 with Fitzpatrick Skin Phototypes V and VI.

Subject Enrollment

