Subjects will be instructed to adopt neutral, non-smiling expressions for each photograph. Images will be taken of each applicable subject with diffuse pigmentation of the face using the Vectra H2 3D Imaging System at Baseline, 1-month post-treatment and 3-months post-treatment. Each subject will have a total of 3 photos taken (right side, left side and center view).

VISIA and/or VISIA-CR (Research Purposes)

Subjects will be instructed to adopt neutral, non-smiling expressions with their eyes gently closed for each photograph. Images will be taken of each applicable subject using the VISIA and/or VISIA-CR at Baseline, 1-month post-treatment and 3-months post-treatment. Subjects will be carefully positioned for each photograph, directly facing the camera for the center view, and turned at a 45° angle for right and left side views. The scan is objectively able to quantify brown spots for assessment and comparison.

Hyperpigmentation Assessment

Skin Hyperpigmentation Index (SHI) (Research Purposes)

The SHI will be calculated using de-identified, cropped images from patient's unaffected skin and patient's hyperpigmented lesions. Images uploaded will be selected from the clinical or lab-based photography the patient has taken at their screening/baseline visit and their 1-month and 3-month follow-up visits. Care will be taken to compare lesions using the same lighting and angles to reduce confounders. The software is able to calculate the relative contributions of pigmentation of each pixel to create a score, and a coefficient is then derived from comparing Pigmentation Scores of the Area with hyperpigmentation versus the Reference Point. This will be used to quantify the change in pigmentation between treatments.

Statistical Methods of Analysis

The per-protocol (PP) population will be the primary population for all statistical analyses. The PP population will include all subjects who received treatment and completed the study in general accordance with the protocol. Only the data of completing subjects will be analyzed.

This study will include descriptive statistics and change from baseline analysis.

The primary outcome of effectiveness will be a paired comparison of baseline to all applicable post-baseline time points for hyperpigmentation and melasma severity using data obtained from VISIA and/or VISIA-CR and the Skin Hyperpigmentation Index results.

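### Preventing iatrogenic dyspigmentation or scarring is part of the primary objective, but no defined endpoint or planned analysis addresses it, and the completers-only rule could remove the affected subjects

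*Combined protocol and SAP*

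**What the plan says.** The primary objective (Purpose and Objective) has two aims. One is to quantify the hyperpigmentation response to the laser. The other is to "explore an effective, adjunctive pre- and post-procedural topical regimen to prevent iatrogenic dyspigmentation or scarring in this population".

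The two primary endpoints are "Quantifying Improvement in overall facial hyperpigmentation in response to laser treatment, by measuring pigmentation at baseline and follow-up visits post-treatment", by VISIA and/or VISIA-CR, and "Changes in Skin Hyperpigmentation Index (SHI) Scores from Baseline to post-treatment visits". The secondary endpoints are "Monitoring incidence, severity, and relatedness of adverse events throughout the study", "Monitoring the efficacy of pre- and post-treatment regimens with tretinoin and hydroquinone" and "Monitor the efficacy of the pre- and post-treatments with Clobetasol and ice". The last two do not say what efficacy means or how it is measured.

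Statistical Methods of Analysis covers descriptive summaries, percent mean change, repeated-measures ANOVA and paired tests, all applied to VISIA and SHI data. It does not mention adverse events. It makes the per-protocol set primary for every analysis and adds: "Only the data of completing subjects will be analyzed".

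Under Adverse Events, staff at each visit "question the subject about adverse events using an open-ended question"; events found on examination are also taken up. Potential Risks lists pigmentary change and scarring as rare or small risks of the laser and gives no rate.

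**The concern.** Prevention of a complication is a question about how many treated subjects develop it. The plan has no case definition, grading, time window, denominator or table for that count. Three things follow.

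- A favourable mean pigment score can coexist with a minority of subjects who worsen.
- The scores are not described as registering loss of pigment or scarring at all.
- A subject who leaves because of the complication may vanish from the analysis, which pushes the result in the favourable direction.

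At stake is whether the final report can say anything reliable about the preventive side of either regimen.

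**Working it through.** The documents give no event rate, SHI variability, effect size, dropout rate or split of the roughly 20 subjects between Parts, so there is no stated figure to reproduce. All shifts and rates below are assumptions.

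**1. Do the planned measures cover the event?**
- SHI runs from 1 (no hyperpigmentation) to 4 and is a ratio of selected hyperpigmented crops to unaffected skin (Hyperpigmentation Assessment; Statistical Methods). It has no value for a scar, and a new lesion outside the crops can be missed. Loss of pigment inside a lesion crop would lower the ratio and read as improvement.
- VISIA is described as quantifying brown spots.

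**2. Can the mean look favourable while some subjects worsen?** Assume n = 20, baseline SHI 2.0, improvers −0.30, and k worseners +0.40.

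Mean change = [(20 − k)(−0.30) + k(0.40)] / 20
- k = 2: (−5.4 + 0.8)/20 = −0.230, or −11.5% of 2.0
- k = 3: (−5.1 + 1.2)/20 = −0.195, or −9.75%
- k = 4: (−4.8 + 1.6)/20 = −0.160, or −8.0%

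The percentage depends on the assumed baseline. For k = 3 it is −0.195/1.5 = −13.0% at a baseline of 1.5 and −0.195/3.0 = −6.5% at 3.0.

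With a within-group SD of 0.20 (assumed; 5,000 simulated trials; paired t-test at 0.05, without the preceding ANOVA), significant improvement appears in 97% of trials for k = 2, 82% for k = 3 and 48% for k = 4.

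**3. What does the completers-only rule do?** Take k = 3 and suppose worseners withdraw.
- None withdraw: 3/20 = 15% affected; mean −0.195 (−9.75%).
- Two withdraw: 1/18 = 5.6%; mean (−5.1 + 0.4)/18 = −0.261 (−13.1%).
- All three withdraw: 0/17; mean −0.300 (−15.0%).

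**4. What would a count show?** Exact (Clopper-Pearson) two-sided 95% limits. For zero events the upper limit is 1 − 0.025^(1/n).
- 0/20: upper limit 1 − 0.025^(1/20) = 16.8%
- 2/20: 1.2% to 31.7%
- 3/20: 3.2% to 37.9%
- 0/10, if a Part had only 10 subjects (an assumption): upper limit 30.8%

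The chance of seeing at least one event in 20 subjects, 1 − (1 − p)^20, is 18% at a true rate of 1%, 33% at 2%, 64% at 5% and 88% at 10%.

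**5. Could the Parts be compared?** Assume rates of 30% and 5% and treat the Parts as independent groups. About 36 per group are needed for 80% power. Fisher's exact test has 9% power with 10 per group and 45% with 20. Part 1 subjects may continue into Part 2, so independence would not hold in any case.

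**The case against.** A reader might infer that no endpoint counts these events, or that an open question is the only way they are captured. The documents do not support either reading. The first secondary endpoint would count dyspigmentation or scarring recorded as an adverse event, with severity and relatedness, and both are named risks. Events found on examination trigger directed questioning, a case report form and photographs. The schedule places a safety assessment at every visit, and the follow-up visits include a skin examination.

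Other points on this side also stand. The SHI endpoint is a change that can go either way. The median, SD, minimum and maximum are planned as well as the mean. The objective's verb is to explore, in a pilot. A higher SHI in a selected lesion may be non-response rather than injury, so the example above does not establish that anyone is harmed.

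These points narrow the concern but do not remove it. The adverse-event count is generic: nothing says when darkening is an event rather than failure to respond, the skin examination has no grading, and the statistical section gives adverse events no analysis. The planned minimum and maximum summarise scores at a visit and do not count subjects who worsened. Whether the completers-only sentence was meant to reach safety data is unclear, but nothing in the text exempts them.

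**Conclusion.** The concern holds in a limited form. One aim of the primary objective has no defined endpoint and no planned analysis. The relevant events can appear only as generic adverse events, and the completers-only rule, taken literally, biases any tabulation towards a favourable answer. In the illustration, 15% of subjects worsen behind a 9.75% mean improvement, and withdrawal of those subjects moves the figures to 0% and 15.0%. The arithmetic is exact, but it rests on an assumed baseline, assumed shifts and assumed withdrawal, so it shows what could happen and not what is expected.

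A reader might also infer that counting the events would let the trial show prevention. It would not: the study has no randomisation and no control group, about 20 subjects, and Parts that may share subjects. A count would give an incidence with an honest interval and would guard against overclaiming.

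**What to change.** In both the endpoint list and the statistical section, add a named secondary endpoint: the number and proportion of all treated subjects, including non-completers, with new or worsened hyperpigmentation, hypopigmentation or scarring through Day 150. State that it is exempt from the completers-only rule.

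- **Definition.** State beforehand how new or worsened pigment is told apart from non-response of the baseline lesion, and how each event is graded.
- **Sources.** Use the safety assessment and adverse-event log at every visit, plus the skin examination and images at Day 90 and Day 150.
- **Reporting.** Report by Part with exact 95% confidence intervals, and give the number of subjects without a Day 90 or Day 150 assessment. Do not pool the Parts as if independent.
- **Objective.** Word the prevention aim as descriptive.

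The cost is a protocol and statistical-section amendment, one definition and one table, with no added visit or imaging. The downsides are wide intervals and thinner information on early leavers. No image is scheduled between the first treatment and Day 90, so a subject who leaves before then contributes safety-assessment data only.

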Following the final treatment, patients should continue to take their 4% Hydroquinone and Tretinoin 0.1% cream as prescribed through the remainder of the study.

Part 2:

Subjects will be asked to refrain from using any topical prescription medications on their face for at least 4 weeks prior to treatments commencing. Subjects who participated in Part 1 will be eligible for Part 2 if they agree to complete the topical regimen washout period and agree to refrain from any other treatments for the remainder of their trial participation.

Pre-Treatment Instructions:

Subjects will be asked to wash off all skincare products at least 30 minutes prior to each scheduled clinic visit using a cleanser of your choice. If a subject arrives having not removed skincare products, she or he will be required to remove the residual product at the clinic and wait at least 20 minutes prior to procedures.

Post-treatment Instructions:

Immediately post-treatment Clobetasol Propionate 0.05% and ice will be applied to the treated areas for 15-20 minutes. The subject will be instructed to re-apply Clobetasol Propionate 0.05% twice a day and ice the treated area for 15 minutes up to four times a day for four days.

Blistering, bleeding, oozing, strong pain, swelling persisting for more than 24 hours, or signs of infection (e.g., pus, drainage, fever) are cause for immediate concern and you should contact the investigator and/or his designee to be evaluated and potentially treated at no cost to the subject.

Subjects will be asked to avoid extended periods of sun exposure and all use of tanning beds for the duration of the study. Extra care should be taken to wear protective clothing and avoid sun exposure from 10 AM to 4 PM.

Subjects will be encouraged to consistently use face wash, moisturizer, and sunscreen of their choosing. Subjects will be asked to refrain from using any new anti-aging, acne, and acne scar products or devices and beginning the use of any new skincare products or devices other than the assigned test material for the duration of the study.

Study Design

Study Timeline and Procedures

Study Procedure		Part 1						Part 2					
		Screening	Treatments			Follow Up		Screening	Treatments			Follow Up	

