A descriptive statistical summary will be provided via the VISIA and/or VISIA-CR. The descriptive statistical summary includes the number of observations (n), mean, median, and standard deviation (SD), minimum (MIN) and maximum (MAX) values at all applicable time points.

A Skin Hyperpigmentation Index is derived automatically using the SHI plug-in. The SHI ranges from 1 (no hyperpigmentation) to 4 (maximum hyperpigmentation) and is a ratio between the Pigmentation Scores of Areas with Hyperpigmentation versus Pigmentation Score of the Reference Point.

The following will be calculated and reported for each evaluation parameter at the applicable post-baseline time point(s):

$$\text{Percent Mean Change from Baseline} = \frac{(\text{Visit Mean Score} - \text{Baseline Mean Score}) \times 100}{\text{Baseline Mean Score}}$$

For each new measurement set we will conduct a repeated measures of analysis of variance (ANOVA) to detect difference between sample distributions. If differences are detected, we will subsequently evaluate specific pairwise comparisons among the post-treatment visit times using a paired T-test or Wilcoxon signed-rank tests. All statistical tests will have a significance level $\alpha=0.05$ (i.e., $p<0.05$). P-values will be reported to 3 decimal places (0.000).

Potential Risks

Standard of Care Risks

Pre-Treatment: Hydroquinone (Rare)

Hydroquinone is a known and effective treatment for hyperpigmentation disorders and is particularly considered to be the standard of care for dermatologic treatment of unwanted hyperpigmentation. Reported adverse effects of hydroquinone administration are uncommon and include short-term cutaneous side effects like irritant contact dermatitis or, with excessive or long-term use or misuse, exogenous ochronosis. Additionally reported side effects include abnormal skin re-pigmentation in continually sun-exposed areas, or trimethylaminuria with chronic use.

Pre-Treatment: Topical Tretinoin (Rare)

Side effects of topical tretinoin are rare and include stinging of the skin, local dryness, hypopigmentation, application site reactions like erythema, irritation, or exfoliation, or, most rare, contact dermatitis or long-term skin changes.

Treatment: Non-Ablative Laser Facial Resurfacing (Rare)

Blistering, burning, scaling and infection (Rare)

A crust, blister or superficial wound can occur in the treatment area. The risk of infection will be minimized by proper wound care.

Bruising (Rare)

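### Laser and regimen efficacy are named as separate endpoints, but follow-up change in each Part measures only the laser-plus-regimen package

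*Combined protocol and SAP*

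**What the plan says.** Under Secondary Endpoints, the protocol lists "Monitoring the efficacy of pre- and post-treatment regimens with tretinoin and hydroquinone" and "Monitor the efficacy of the pre- and post-treatments with Clobetasol and ice". Primary endpoint 1 describes improvement in facial pigmentation as a response to the laser, and the background, just before Purpose and Objective, gives the study's aim as quantifying how well this laser works in phototypes V and VI.

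The Overview of Clinical Study calls the trial a "single-site, prospective observational, non-randomized, non-controlled pilot study". The exposures are:

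- **Part 1:** "Study doctors will explain and prescribe subjects a standard of care topical regimen 4-6 weeks prior to f1927 treatments". Three laser sessions follow at Days 0, 30 and 60. Subject Instructions continue hydroquinone and tretinoin after the last session until the study ends.
- **Part 2:** the pre-laser instruction is "Subjects will be asked to refrain from using any topical prescription medications on their face for at least 4 weeks prior to treatments commencing". The same three sessions follow, and after each one "Immediately post-treatment Clobetasol Propionate 0.05% and ice will be applied to the treated areas for 15-20 minutes", with home use for four days.

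Photography Procedures and the Skin Hyperpigmentation Index section take images at screening/baseline and at the 1-month and 3-month follow-ups (Days 90 and 150). Statistical Methods of Analysis plans descriptive statistics, change from baseline, repeated-measures ANOVA and paired tests at a significance level of 0.05. It contains no comparison between Parts and no analysis assigned to secondary endpoints 2 and 3.

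**The concern.** No subject in either Part has the laser without a regimen, and no subject is followed to Day 90 or 150 on a regimen without the laser. The change from baseline in a Part therefore belongs to the combination. In Part 1 this matters for the primary endpoint too, because the risk section states that "Hydroquinone is a known and effective treatment for hyperpigmentation disorders". The baseline image precedes that drug, and both follow-up images are taken while subjects are still meant to be using it.

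If the endpoints stay as worded, the same Part 1 mean change could be reported once as a response to the laser (primary endpoint 1) and again as efficacy of hydroquinone/tretinoin (secondary endpoint 2). The data could not support either attribution.

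Endpoint 3 has a separate inconsistency. It refers to Clobetasol and ice before as well as after treatment, whereas the Part 2 narrative describes them only after the laser.

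**Working it through.** The protocol gives no effect size, standard deviation or power figure (only about 20 subjects), so there is no stated number to reproduce. The question is which effects the design can identify.

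**Step 1: follow-up change from screening.** Let L be the laser effect, H that of hydroquinone/tretinoin and C that of Clobetasol/ice. To be generous to the plan, assume additive effects and no time trend, regression to the mean, order or carry-over effect.

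- Part 1 change = L + H, design row (1, 1, 0).
- Part 2 change = L + C, design row (1, 0, 1).

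Each Part alone has rank 1 for two unknowns. Pooled, the rank is 2 for three unknowns. For any k, replacing L by L + k, H by H − k and C by C − k leaves both expected changes the same, so none of the three effects is identified at any sample size. Only H − C, the Part 1 change minus the Part 2 change, is identified, and the plan does not include that contrast.

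**Step 2: how clean H − C would be.** The Parts run in sequence without randomisation. Part 2 mixes subjects continuing from Part 1, who have already had three laser sessions, with new subjects. Part 2 screening comes before the washout, so for a continuing subject a screening baseline also brings in the effect of stopping hydroquinone and tretinoin. Post-laser cooling is at the provider's discretion in both Parts, so cooling is not confined to Part 2.

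**Step 3: the Day 0 image.** The Part 1 visit text calls for imaging at screening, before prescriptions are sent, and again before the first laser session. Split H into Hpre and Hpost.

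- Screening to Day 0 = Hpre.
- Day 0 to follow-up = L + Hpost.

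Over (L, Hpre, Hpost) the rows are (0, 1, 0) and (1, 0, 1), rank 2 of 3. Hpre becomes estimable if nothing else changes pigmentation over those weeks; L and Hpost stay combined. In Part 2 the interval before Day 0 is a washout, so the same image says nothing about Clobetasol.

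The schedule table under Study Timeline and Procedures, Photography Procedures and the Skin Hyperpigmentation Index section do not list a Day 0 image, and the statistical section does not use one.

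**Step 4: extent of the overlap in Part 1.** On nominal days, screening to Day 150 spans 28 + 150 = 178 to 42 + 150 = 192 days. Hydroquinone is prescribed for 28 to 42 days before the laser and for 150 − 60 = 90 days after the last session. That is 118 to 132 days, or 118/178 = 66% to 132/192 = 69% of the interval, leaving aside any use between sessions. This shows how far the exposures overlap. It does not measure any effect.

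**Step 5: endpoint 3 beside the procedures.** Purpose and Objective, Overview of Clinical Study, Subject Instructions and the Part 2 treatment visits all place Clobetasol and ice after the laser. Part 2 subjects are asked to use no prescription facial topical for at least 4 weeks beforehand.

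**The case against.** The strongest reply is that this is an openly uncontrolled pilot. The secondary endpoints speak of monitoring, the objective speaks of exploring, and the analysis is mostly descriptive. That stands as far as it goes: the lack of a control is disclosed, and nothing in the protocol promises a statement that a regimen worked by itself. A reader might infer that the plan sets out to prove each regimen's efficacy, and the text does not support that. Even so, the endpoints name efficacy, primary endpoint 1 names the laser, tests are run at 0.05, and no sentence limits the conclusions.

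A second reply is that the regimens are meant to prevent dyspigmentation or scarring after the laser, not only to lighten pigment. This is correct, and rewording must keep it. It does not remove the problem: crediting prevention to a regimen also needs a comparator, and no measure is defined for either endpoint.

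A third reply is that some subjects complete both Parts, which gives within-subject data. This could support an exploratory comparison, subject to the limits in Step 2.

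Two further readings go too far. One is that nothing about any regimen can be separated; the Day 0 image in the visit text gives a partial, uncontrolled view of the Part 1 pre-treatment phase. The other is that it is settled that no subject has Clobetasol before the laser. The narrative is consistent on this, but the Clobetasol/ice row of the schedule is not legible in the text available, so the point is an inconsistency to reconcile.

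**Conclusion.** The concern holds for all follow-up results. Change from screening to Day 90 or 150 estimates laser plus hydroquinone/tretinoin in Part 1 and laser plus Clobetasol/ice in Part 2. Neither the laser effect nor either regimen's full effect can be recovered from these data at any sample size: rank 2 for three effects, even assuming additivity and no time, order or carry-over effects.

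The exception is the pre-treatment phase of the Part 1 regimen, and only if the Day 0 images are taken. That change would be before-after without a control. It may not be free of earlier laser effect either, because inclusion criterion 3 refers to 1927nm laser treatment within the preceding 3 months.

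A reader might compare days of pre-laser hydroquinone with days of Clobetasol to argue that the packages are unequal. Those are different drugs in different phases, and the comparison has no bearing on what is identifiable.

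The fault is in what the endpoints say can be learned. It can be put right without changing what subjects receive.

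**What to change.** 1. Reword primary endpoint 1, the aim in the background, and secondary endpoints 2 and 3 as outcomes of the laser together with the regimen, reported separately for Part 1 and Part 2. Keep the stated aim of preventing dyspigmentation or scarring.
2. Reconcile the Day 0 imaging across the schedule table, the treatment-visit text, Photography Procedures and the Skin Hyperpigmentation Index section. Where the images are taken, report Part 1 change from screening to Day 0 and from Day 0 to each follow-up descriptively.
3. Add to Statistical Methods of Analysis that no confirmatory conclusion will be drawn on the laser alone, on a regimen alone, or on one regimen against the other, and that any Part 1 versus Part 2 comparison is exploratory.
4. Reconcile the wording of endpoint 3 on Clobetasol and ice before treatment with Purpose and Objective, Overview of Clinical Study, Subject Instructions and the Part 2 treatment visits.

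The cost is narrower claims. Items 1, 3 and 4 are wording, and item 2 uses images that the visit text already requests.

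A concurrent laser-only group would make all three effects estimable (rank 3), but it is not a realistic repair at this size. Assuming independent groups, two-sided 0.05 and 80% power, the detectable standardised difference is (1.960 + 0.842) × √(2/n). This gives 1.62 at n = 6 and 1.50 at n = 7 per group, which is about 20 subjects split three ways.
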